WP4Ruminative ResponseScale-Brooding(RRS-B;(Nolen-hoeksema & Morrow,1991)Assessrisk,personalisation,predictor,predictor,secondaryOutcome	The brooding subscale of the RRS (Nolen-hoeksema & Morrow, 1991) is used as a "depression-independent" scale which measures dysfunctional rumination. The scale consists of 5 items which can be rated from '1' (never) to '4 (always), resulting in a total score from 5 to 20. Versions available in English, German, Dutch, Spanish	Higher levels of brooding predict depression (Treynor et al., 2003; Moberly & [name], 2008). Internal consistency for the brooding subscale is Cronbach's alpha = .75 (Schoofs et al., 2010). In the Ghent sample: RRS-B: .72 (5 items, N=737 associated with more depression in longitudinal analyses (Treynor, Gonzalez & Nolen-Hoeksema, 2003) Correlated with depressive symptoms concurrently (r = 0.54, p < 0.01) and six months later (r = 0.49, p < 0.01) (Samtani & Moulds, 2017)
Penn State Worry Questionnaire (PSWQ-A ; Hopko et al., 2003) Assess risk, personalisation, predictor, secondary Outcome	The PSWQ-A (Hopko et al., 2003) is an abbreviated 8-item version of the original 16-item questionnaire that aims to measure the trait of worry, using Likert rating from 1 (not at all typical of me) to 5 (very typical of me). Research suggests that the instrument has a strong ability to differentiate patients with generalized anxiety disorder (GAD) from other anxiety disorders. Available in English, Spanish, German, and Dutch versions.	Cronbach's alpha = .89 for the PSWQ-A (Kertz et al., 2014), in the Ghent sample: PSWQ-A: .92 (8 items, N=738) e.g., predicted future symptoms of anxiety and depression. (Topper et al., 2014) "Rumination and worry are partly responsible for the cross-sectional and prospective co-occurrence of

Measure	Description	Reliability and Validity
		affective disorders and may be suitable targets for treatment" (Drost et al., 2015).
WP5		
CEUT	The CEUT-S is a shortened form of the CEUT – The Components of Emotion Understanding Test which was developed on the basis of the Componential Emotion Approach. Participants read a series of emotion eliciting situations each containing emotional reactions that align with emotion components. The participant rates the likelihood of each emotional reaction in the situation on a 5-point response scale (Very unlikely, Unlikely, Neither likely/Nor unlikely, Likely, Very likely). The original form (also called SASTEU) has 10 situations in which participant rates 30 questions per situation (300 items). The shortened form contains 7 emotion eliciting situations and 6 emotional reactions (42 items). For ECoWeB purpose, this was further reduced to 6 scenarios with 4 questions each (24 items)	The only measure that assesses understanding of all five emotion components of the Componential Emotion Approach (appraisals, action tendencies, bodily reactions, expression, subjective feelings). Test has been validated with Black and White students in South Africa. The test has a good reliability (Cronbach's alpha of.89). The test correlated with verbal ability, self-report emotional intelligence, emotionality, extraversion, conscientiousness, openness to experience, positive affect, and self-esteem, and was negatively correlated with somatic complaints (Sekwena & Fontaine, 2017).
Geneva Emotion Recognition Test Short (GERT-S) GERTS-20	GERT-S is a 42-item performance-based emotion recognition test in which participants view short video clips of actors expressing 14 different emotions. After each clip, participants choose which of 14 emotions had been expressed by the actor. For Ecoweb, a very brief version of this original brief test with 20 items was created Schlegel, K., & Scherer, K. R. (2016). Introducing a short version of the Geneva Emotion Recognition Test (GERT-S): Psychometric properties and construct validation. Behavior Research Methods, 48(4), 1383–1392. The GERT was originally developed from the Geneva Multimodal Emotion Portrayals (GEMEP) corpus (Bänziger et al., 2012), which contains 1,260 audio-video clips (duration 1–4 s) of 18 emotions portrayed by 10 actors with different intensities	The GERT-S reached Cronbach's alphas of about .80 in several samples in different languages. It is a Rasch-homogeneous and unidimensional test. It correlates as expected with other measures of emotional intelligence, personality, alexithymia, intelligence etc. (see Schlegel, Fontaine, & Scherer, 2017; Schlegel & Scherer, 2016). For the very brief 20 item version, the items with the best item discrimination parameters were chosen based on data from various studies. Reliability of this version is unknown.

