ASRQ = Social rejection questionnaire	Rejection Sensitivity Questionnaire (ARSQ; Berenson et al., 2009). Rejection sensitivity (RS) is a cognitive-affective processing disposition to anxiously expect rejection, shaped by cognitive social learning history and triggered in situations when either rejection or acceptance is possible. The RS-Adult questionnaire (A-RSQ) is an adaptation of the RSQ (Downey & Feldman, 1996) for assessing RS in adult research participants. It consists of 9 scenarios describing social situations/requests (e.g., You call a friend when there is something on your mind	Strong psychometric properties and may potentially be an equally good measure of negative appraisal biases in young people. Internal consistency (alpha) = .89 (for each administration) Test–retest reliability (Spearman– Brown coefficient) = .91 Scores were significantly higher in the borderline personality disorder group (M =14.86, SD=6.09) than in the healthy comparison group (M = 6.19, SD = 2.80), t (63.4) = 8.58, p < .001.

Measure	Description	Reliability and Validity
WP4	that you feel you really need to talk about), each of which is rated for level of concern or anxiety that the relevant person would not respond positively ("rejection concern"), rated on a 1 to 6 scale from 1 "very concerned" to 6"very unconcerned", and for expectation that the other person would accept the request and respond positively ("acceptance expectancy"), rated on a 1 to 6 scale from 1 "very unlikely" to 6 "very likely". This "acceptance expectancy" is reverse scored, i.e., 7- acceptance expectancy to provide an index of rejection expectancy. Overall rejection sensitivity is calculated by multiplying rejection expectancy by rejection concern. On the basis of the results of the analysis of the validation studies the number of scenarios has been reduced from 9 to 8.	Berenson, Downey, Rafaeli, Coifman & Paquin (2011). The rejection-rage contingency in borderline personality disorder. Journal of Abnormal Psychology, 120, 681-690.

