3.7 Endpoints/outcomes

Table 16 Endpoints/outcomes

The following table displays which measures are collected at each of the assessment points:

Work	Measure	Detail	Size	Base	4	3	12
Pckge				line	weeks	months	months
6/7	Pre-screening	Language	1 item	Х			
	(pre consent)	Country under which participating,	5 items				
		Gender, ethnicity, confirmation of likely eligibility re current mental health		x			
6/7	Age Screening	Date of birth	1 item	x			
6/7	WEMWBS	Primary outcome measure (ECoWeb- PROMOTE); secondary outcome (ECoWeB- PREVENT)	14-item	Х	X	Х	X
6/7	LIDAS current and past	Screening for past depression	Conditional questionnaire asked ever and last 3 months ranging 4	X, Last 3 months,		X, last 3 months	X, last 12 months
	inclusion exclusion		questions to 22 depending on answers	and ever			
	criteria items		3 Conditional risk questions				
			7 other items				
			On past health;				
6/7	PHQ9	Primary outcome (ECoWeB-PREVENT), secondary outcome (ECoWeB-PROMOTE)	9-item plus 3 conditional risk questions	x	x	Х	Х

			parental past health 2 items				
End of	screening and st	art of EC/risk of measures					
6/7	GAD7	Secondary outcome measure	7-item	Х	Х	Х	Х
WP4	RRS Brooding	Used for EC. Used for risk and personalisation algorithm	5 items	x	x	x	x
WP3b	Rejection	Used for EC	16 items	х	x	х	х
	sensitivity questionnaire	Used for risk and personalisation algorithm					
6/7	WSAS	General Functioning	5-item	Х	Х	Х	Х
WP4	PSWQA short	Used for EC	9 items	x	x	х	x
	form	Used for risk and personalisation algorithm					
WP5	GERT	Used for EC	20 videos	x	x	х	x
	(Geneva Emotion	Used for risk and personalisation algorithm					
	Recognition						
WP5	Task) CEUT-short	Used for EC	6 items with 4 options				
VVF3	form		o items with 4 options	X	x	x	x
		Used for risk and personalisation algorithm					
6/7	Demographics	Self-educational level,	2 questions in 6 parts	X	Status	status	status
					only	only	only
WP3b	Achievement	Used for EC	14 items in 3 versions	x	x	x	x
	Appraisal	Used for risk and personalisation algorithm					

WP3b	Achievement Emotion Questionnaire	Used for EC Used for risk and personalisation algorithm	12 items in 3 versions	x	x	x	x
6/7	EQ5-D3L	Quality of Life	6-item	Х		Х	Х
WP6	ADSUS- adapted Physical health demographic	Estimate of health costs	2-14 items 1 item	X (excludi ng anxiety and depressi items)		X 3mth	X 12mth
End of s	screening/tailoring	measures and start of additional measures					
WP 3a	EMO Dis	Control	4 items				
	control belief scale						

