## 3. Study methods

#### 3.1 Trial design

Both PROMOTE and PREVENT are 3-arm parallel group trials, with individual randomisation in a 1:1:1 ratio. For both trials, an external pilot will be carried out to identify any issues in the administrative aspects of the trial, such as participant recruitment, consent procedures for under 18s (in countries where parental consent is required for trial participation of under-18s. The data from this pilot will not be combined with the results of the main trials, which are fully powered definitive trials. Furthermore, the external pilot has no stopping criteria that would, if fulfilled, lead to the main trial being cancelled prior to commencement.

The usual care intervention comprises only self-monitoring using the app. The personalised active intervention consists of usual care plus two out of four modules for emotional competence self-help training, selected for each participant. The standard active intervention consists of usual care plus a self-help intervention based on CBT principles, also delivered via the app.

The ECoWeB trials will be performed within the framework of a cohort multiple RCT (cmRCT). A top level cohort of potential participants, whose eligibility for either PROMOTE or PREVENT has been established, will be recruited. These participants will consent to participating in the cohort and to being offered potential treatments if applicable via the screening website. Based on their baseline scores on eight measures (collected at baseline), to be converted to z-scores (using means and standard deviations derived from a validation study across all four sites), the participant will be allocated to either PROMOTE (lower risk of mental health problems) or PREVENT (higher risk of mental health problems). Full details of the process for allocation of participants to either PROMOTE

or PREVENT are reported elsewhere (Trial selection, randomisation, selection of emotional competence intervention components document).

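### Table 14's printed anchors and formula for the rejection-sensitivity score contradict each other, and the score feeds the risk and personalisation algorithm

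*Protocol*

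**What the plan says.** Table 14 in Protocol section 3.3 describes rejection sensitivity as "a cognitive-affective processing disposition to anxiously expect rejection". Each scenario gets two ratings.

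- **Concern:** the scenarios are "each of which is rated for level of concern or anxiety that the relevant person would not respond positively", and this is "rated on a 1 to 6 scale from 1 'very concerned' to 6'very unconcerned".
- **Acceptance expectancy:** "rated on a 1 to 6 scale from 1 'very unlikely' to 6 'very likely". This rating is reversed as 7 minus the rating, giving rejection expectancy.

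The total is then defined: "Overall rejection sensitivity is calculated by multiplying rejection expectancy by rejection concern". No reversal of the concern rating is stated in either document. As evidence of validity the table reports that "Scores were significantly higher in the borderline personality disorder group" (mean 14.86, against 6.19 in the healthy comparison group).

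Table 16 in Protocol section 3.7 lists the questionnaire with 16 items, which matches 8 scenarios with 2 ratings each. It is scheduled at all four assessments and marked "Used for risk and personalisation algorithm". SAP section 3.1 describes assignment to PROMOTE or PREVENT: "Based on their baseline scores on eight measures (collected at baseline), to be converted to z-scores". The same section says that modules in the personalised arm are chosen from 11 measures. It names neither set of measures and refers to a separate document for the details.

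**The concern.** A score for anxious expectation of rejection should be highest when a person is both anxious and expects rejection. The printed rule multiplies a correctly directed factor (rejection expectancy) by one that runs the wrong way (concern, where 6 means unconcerned). Because the table spells out one reversal, a programmer would reasonably use the other rating raw.

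Three things depend on the score. It helps decide whether a participant enters PROMOTE or PREVENT, and so which primary outcome applies. It helps decide who in the personalised arm receives the Social appraisal module, whose content (Protocol section 8) targets perceived rejection. It is also one of the emotional-competence measures that Protocol sections 3.3 and 10.7 treat as potential mediators. Protocol section 6 bases risk thresholds on the worst quartile or tertile of each measure, so errors in the upper tail matter most.

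**Working it through.** **Inputs.** All come from Table 14. Let c be the concern rating (1 = very concerned, 6 = very unconcerned), a the acceptance rating, and e = 7 - a the rejection expectancy.

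- Printed score: e x c
- Score with concern reversed: e x (7 - c)

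**Corner profiles**

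| Respondent | c | a | Printed | Concern reversed |
|---|---|---|---|---|
| Very concerned, expects rejection | 1 | 1 | 6 x 1 = 6 | 6 x 6 = 36 |
| Very unconcerned, expects acceptance | 6 | 6 | 1 x 6 = 6 | 1 x 1 = 1 |
| Very unconcerned, expects rejection | 6 | 1 | 6 x 6 = 36 | 6 x 1 = 6 |
| Very concerned, expects acceptance | 1 | 6 | 1 x 1 = 1 | 1 x 6 = 6 |

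The printed rule ties the two opposite ends of the construct at 6. With rejection fully expected, it gives 36, 30, 24, 18, 12, 6 as concern rises from least to most. The reversed rule puts the construct's extremes at 36 and 1, which fits both the definition and the higher clinical mean.

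**Agreement over all 36 response pairs, equally weighted.** E[e] = E[c] = 3.5 and E[e²] = 91/6 = 15.167, so E[c(7 - c)] = 24.5 - 15.167 = 9.333.

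- Covariance of the two scores: 15.167 x 9.333 - 3.5⁴ = 141.56 - 150.06 = -8.51
- Variance of each score: 15.167² - 3.5⁴ = 230.03 - 150.06 = 79.97
- Correlation: -8.51 / 79.97 = -0.11

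**Why z-scores do not repair it.** Since e(7 - c) = 7e - ec, the reversed score equals 7e minus the printed score. The term 7e differs between people, so neither a sign change nor a linear rescaling recovers the intended score.

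**Realistic response patterns (illustrative).** The documents give no item distributions, so these figures rest on assumptions: 8 scenarios, mean concern 3.0 to 3.5 (scored so that high is anxious), mean rejection expectancy 2.5 to 3.0, the two ratings positively related, and item scores averaged. Across several such simulations:

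- The printed and reversed scores correlated between -0.05 and 0.37.
- Between 19% and 37% of the true worst quartile fell in the worst quartile of the printed score (25% by chance).
- In the single-trait version with loadings 0.3, 0.5 and 0.7, correlation with the trait was 0.17, 0.28 and 0.41 for the printed score, against 0.75, 0.89 and 0.93 for the reversed score.

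**Effect on trial assignment (illustrative; the actual rule is not in the documents).** Assume an equally weighted sum of eight z-scores, the worst 30% sent to PREVENT, correlation between measures of 0.1 to 0.5, and only this measure mis-scored. About 5% to 11% of participants would then change trial. A different rule would give a different figure.

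**The case against.** The strongest reply is that Table 14 describes instruments and is not the operative algorithm. Trial assignment and module selection are specified in a separate document, and SAP section 6.1 places reverse coding for its listed outcomes in the Data Dictionary. Neither was available. The table also names the rated quantity as concern and multiplies by concern; if 6 simply meant very concerned, the formula would be right and would agree with the cited means. A swapped pair of anchor words is quite possible. Similar slips occur elsewhere: Table 13 calls WEMWBS a 4-point scale but lists anchors 1 to 5, and the worry questionnaire has 8 items in Table 14 and 9 in Table 16.

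This stands as a limit on the consequence: nothing shows that the printed scoring was deployed. It does not remove the contradiction. Table 14 is the only place in the two documents where this score is defined, and following it exactly gives a wrong score.

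It is also fair that the questionnaire is one input among several. Table 16 marks at least six other instruments for the same algorithm, so single-measure overlap figures overstate the effect on trial membership.

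**Conclusion.** The printed anchors, the formula and the cited direction of the score cannot all hold. That follows from Table 14 alone and needs no assumption. The consequence for the trial is conditional. If the printed rule was live, this marker would carry little of the intended information, some participants would be placed in the other trial, and some Social appraisal modules would be mismatched. The size depends on the unseen algorithm; 5% to 11% changing trial is an illustration under the rule stated above.

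Three stronger readings might be inferred, and the documents do not support them.

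- **That participants were in fact misassigned.** The fielded items and code are not described, so this is unknown.
- **That the treatment comparisons are biased.** Randomisation follows trial assignment, so between-arm contrasts within each trial remain valid. The questionnaire is also absent from the outcome list in SAP section 6.1. What could change is who makes up each trial, how well modules match in one arm, and any analysis using the score as an emotional-competence outcome or mediator.
- **That the printed score is pure noise.** Its expectancy half is correctly directed, so a weak relation to the trait can remain.

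**What to change.** 1. Check the concern anchors and the scoring in four places: the fielded Qualtrics items, the Data Dictionary, the validation-study means and SDs used for the z-scores, and the trial-assignment and module algorithm. Norms and trial data must use the same scoring.
2. If the item was fielded with 6 = very concerned, correct the anchors in Table 14.
3. If it was fielded as printed, score concern as 7 minus the rating before multiplying, and state this in Table 14 and wherever the score is computed. Keep the instrument's existing rule for combining scenarios; Table 14 does not state one, so it should be written down at the same time.
4. If the printed scoring was live, keep every participant in the trial in which they were randomised. Rescore from the stored items for emotional-competence and mediation analyses, and report how many participants would have changed trial or module.

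The cost is a check of existing materials and, at most, one line of scoring code plus a short descriptive table. No new data collection is needed, because the assessment responses are already held in the trial database (Protocol sections 7 and 11.1).

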3.4 Primary endpoint/outcome

The primary endpoint of the trial is at 3 months post randomisation.

All participants will have had the opportunity to use the App for 3 months at their own discretion so at that point the trial is powered to see if the personalised Emotional Competence self-help is superior to the CBT self-help (active control) and to the usual care self-monitoring control in promoting well-being (ECoWeB-PROMOTE trial) or preventing poor mental health (ECoWeB-PREVENT trial). The 3month primary endpoint was chosen:

a. to maximise power and sensitivity to intervention as closer to actual use of intervention

b. to reduce the negative impact of drop-out attrition on study power

c. to increase comparability to other studies using mental health apps as this is a typical endpoint in app interventions

d. to provides a proof-of-principle of changes in known predictors/analogues of poor mental health such as depression and anxiety – i.e., if we can show change in depression symptoms, rumination or other EC measures at 3 months, then we are likely to predict the future impact of the intervention on the onset of future emotional disorders. This can be checked at the 12month follow up (i.e., this is consistent with a prevention-mechanism trial – Zalta & Shankman 2016). Prevention Mechanism trials are deemed successful if an intervention reduces well-established risk factors for development or maintenance of psychopathology or increases established resilience factors. Such trials may help identify novel interventions that target multiple known risk factors, and in turn, strategies most likely to reduce dysfunction.

e) there is an expectation of relatively high attrition by the 12month follow-up due to competing demands on the attention and motivation of young adults. The Youth Advisory Board advised that staying in the trial for 3 months would be reasonable, but they might lose interest over a longer period. The highest number of participants returning follow ups is likely to be at 3 months.

3.5 Secondary endpoints

The secondary endpoint is the 12 month follow up for all trials, which is included to test if any effects found at the primary endpoint are maintained over time. Because any change in the symptoms of poor mental health may take time to manifest, the 12month follow-up will also be used as a secondary outcome to test if there is medium-term effect of the active interventions on improving well-being and reducing poor mental health (depression, anxiety), relative to the control arms.

3.6 Exploratory endpoints

There are no exploratory endpoints.

3.7 Endpoints/outcomes

Table 16 Endpoints/outcomes

The following table displays which measures are collected at each of the assessment points:

Work	Measure	Detail	Size	Base	4	3	12
Pckge				line	weeks	months	months
6/7	Pre-screening	Language	1 item	Х			
	(pre consent)	Country under which participating,	5 items				
		Gender, ethnicity, confirmation of likely eligibility re current mental health		x			
6/7	Age Screening	Date of birth	1 item	x			
6/7	WEMWBS	Primary outcome measure (ECoWeb- PROMOTE); secondary outcome (ECoWeB- PREVENT)	14-item	Х	X	Х	X
6/7	LIDAS current and past	Screening for past depression	Conditional questionnaire asked ever and last 3 months ranging 4	X, Last 3 months,		X, last 3 months	X, last 12 months
	inclusion exclusion		questions to 22 depending on answers	and ever			
	criteria items		3 Conditional risk questions				
			7 other items				
			On past health;				
6/7	PHQ9	Primary outcome (ECoWeB-PREVENT), secondary outcome (ECoWeB-PROMOTE)	9-item plus 3 conditional risk questions	x	x	Х	Х

			parental past health 2 items				
End of	screening and st	art of EC/risk of measures					
6/7	GAD7	Secondary outcome measure	7-item	Х	Х	Х	Х
WP4	RRS Brooding	Used for EC. Used for risk and personalisation algorithm	5 items	x	x	x	x
WP3b	Rejection	Used for EC	16 items	х	x	х	х
	sensitivity questionnaire	Used for risk and personalisation algorithm					
6/7	WSAS	General Functioning	5-item	Х	Х	Х	Х
WP4	PSWQA short	Used for EC	9 items	x	x	х	x
	form	Used for risk and personalisation algorithm					
WP5	GERT	Used for EC	20 videos	x	x	х	x
	(Geneva Emotion	Used for risk and personalisation algorithm					
	Recognition						
WP5	Task) CEUT-short	Used for EC	6 items with 4 options				
VVF3	form		o items with 4 options	X	x	x	x
		Used for risk and personalisation algorithm					
6/7	Demographics	Self-educational level,	2 questions in 6 parts	X	Status	status	status
					only	only	only
WP3b	Achievement	Used for EC	14 items in 3 versions	x	x	x	x
	Appraisal	Used for risk and personalisation algorithm					

WP3b	Achievement Emotion Questionnaire	Used for EC Used for risk and personalisation algorithm	12 items in 3 versions	x	x	x	x
6/7	EQ5-D3L	Quality of Life	6-item	Х		Х	Х
WP6	ADSUS- adapted Physical health demographic	Estimate of health costs	2-14 items 1 item	X (excludi ng anxiety and depressi items)		X 3mth	X 12mth
End of s	screening/tailoring	measures and start of additional measures					
WP 3a	EMO Dis	Control	4 items				
	control belief scale						
WP3a			4 scenarios with 6ratings each, 24 questions	x	x	x	×
WP3a 6/7	scale Emotion reaction			X X	x	x	x

